including seizure frequency, seizure type, seizure onset, medication history, family history of seizure, and also developmental stages, will be recorded from electronic medical record. Besides, the CT-scan or MRI are also collected from the same source. After that, their quality of life will be assessed by QOLCE-55 validated questionnaire through self-guided report. Furthermore, the laboratory investigation and EEG will be performed.

The next phase is intervention phase, started from initial step and ended by the maintenance of new combination therapy, which takes with overall 12 weeks. Initially, the substitution drugs with each initial dose are consumed. The drugs consist of valproic acid for the generalized and carbamazepine for focal epilepsies. On the other hand, the control group will take lamotrigine or clobazam for generalized and oxcarbazepine for focal ones. The phase continuous to titration dose, in which, the dose is raised gradually until it causes 50% of seizure reduction, and the next step is maintained the dose for about 2 weeks.

The following is tapering-off and after that stopping the substituted drug, levetiracetam or topiramate, which is determined by considering individual condition. Yet, if the seizures increase more than one and a half time of the previous frequency during the phases, the intervention will be ended immediately. On the contrary, if the condition is better, then the children go to the maintenance of new combination, that is the substitution drug and the old drugs in which the seizures do not go up or even better keep going down. The children who complete all of the phases are categorized as responder. In case if the intervention is ended, the subjects will be given the former combination therapy with adjusted doses in order to decrease the seizures until reaching the pre-intervention condition. The subjects are categorized as non-responder, and will be dropped-out. The other criteria of drop-out are resignation, non-compliance of study procedure, and death in term of other causal not related to the study. While in term of lost to follow-up, is intended for those who do not attend the study without any possible reasons.

[figure not shown]

Figure 2. flow-chart of the study

Maintenance the dose of the new combination therapy that consist of the new drug and

Maintenance

old drug after stopping the substituted drug

Inclusion criteria

- 1. Children age at 1 18 years old

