EEG recording results are categorized into:

- Normal: does not show of hypofunction/asymmetry/epileptiform waves
- Abnormal: shows a picture of hypofunction/asymmetry/epileptiform waves or a combination of 1 or more of these features

The subjects who show changes in their EEG are later grouped into groups of abnormal to normal or abnormalities that showed improvement. Abnormalities that show improvement, for example are hypofunction (slowing down) waves experience improvement or decreasing number of epileptiform waves.

Next, a proportion calculation is carried out in the form of the percentage to subjects who experience a change in the EEG and will be categorized into:

- Different : when a significant difference is shown in difference of proportion test of the group that reuses first line OAE line as substitution therapy and those that use standard therapy/
- Not different: when there is no significant difference is shown in difference of proportion test of the 2 groups.
- d. Difference in actual failure between the groups reusing first line OAE as substitution therapy and those taking standard therapy. Description of drug side effects in the form of frequency distribution and percentage of side effects in each group. Description of laboratory results in the form of frequency distribution and percentage of side effects in each group
- e. Factors contributing to decrease in seizure frequency (age, seizure onset, seizure type, family history of seizures, developmental delay, history of OAE, initial seizure frequency, initial EEG, structural brain abnormalities)

Sample size

The estimated sample size in this study was calculated using the different proportion formula for the 2 unpaired groups as follows ²⁹:

$$n1 = n2 = (\frac{Z_{\alpha}\sqrt{2PQ} + Z_{\beta}\sqrt{P1Q1 + P2Q2}}{P1 - P2})^{2}$$

Description:

n1 number of subjects who received the new drug (First Line OAE)

n2 number of subjects receiving standard drug (Second line OAE)

Alpha type one error (5%)

Zα alpha standard value 5% one-way hypothesis (1,96)

Beta type two error (20%)

Zβ beta default value 20% (0,84)

P2 proportion of decreased seizures on standard drugs (reference) for example 0.7

Q2
$$1-P2 = 1-0.7 = 0.3$$

P1-P2 difference in the proportion of reduced seizure that is considered significant between the new drug and the standard (defined by the researcher) for example 25% (0.25)

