P1 proportion of reduced seizure on the new drug (the proportion of reduced seizure on the standard drug in addition to the minimal difference that is considered significant)= 0.7 + 0.25 = 0.95

Q1
$$1 - P1 = 1 - 0.95 = 0.5$$

P
$$(P1 + P2) / 2 = (0.95 + 0.7) / 2 = 0.825$$

Q
$$1-P = 1-0.825 = 0.175$$

In this study, it was found that the proportion of seizure reduction on standard drugs was 70%.³⁰ Therefore the equation:

$$n1 = n2 = \left(\frac{1,96\sqrt{2(0,825)(0,175)} + 0,84\sqrt{(0,95)(0,5) + (0,7)(0,3)}}{0,25}\right)^2 = 49,56 = 50$$

$$n\ 2\ groups=100$$

Based on the formula above, 100 research subjects are required. An additional of 10% from the total number of subjects are needed as there is a possibility of those dropping out, therefore a total of 110 subjects are needed in this study.

Statistical Analysis

- 1. Analysis of differences in the proportion of responders (primary outcome), differences in EEG appearance (secondary outcome) in pediatric epilepsy patients who are resistant to the combination of second line OAE between those who reused first line OAE as substitution therapy and those who used standard therapy. Data type is categorical. Data is analyzed the Chi-square statistical test, if it does not meet the requirements then an alternative test is performed, known as Fisher's multiple test. The significance level (α) is 5% and the research confidence level is 80%. If p value ≤ α is obtained, this means H0 is rejected, which means that there is a difference seen in seizure frequency between reusing first line OAE as substitution therapy and standard therapy.
- 2. Analysis of differences in the mean quality of life with an unpaired T test if the data distribution is normal or Mann-Whitney if data distribution is not normal
- 3. To assess drug effectiveness, the analysis used was the difference in actual failure between those using first line OAE as substitution therapy and those using standard therapy (primary outcome). Formula:

$$ARR = CER - EER$$

CER: the incidence of increased seizure frequency in the standard therapy group ERR: the incidence of increased seizure frequency in the group in substitution therapy with 1st line OAE The increase in seizure frequency in this study shows therapy

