This test will use 2 analyses known as intention to treat analysis and per-protocol analysis. Intention to treat analysis means that all research subjects who have been randomized are included in the analysis according to their initial allocation regardless of whether or not the subject is taking the drug/therapy being tested or a placebo, or whether these subjects died before taking the drug being tested. Subjects who did not

failure.

take medication, lost to follow-up, and who moved to another group, are considered failures of their original group.

Whereas per protocol analysis only includes subjects who complete the research to the end.

- 4. Analysis of the difference in time to achieve a decrease in seizure frequency with the chisquare test or if it does not meet the requirements, an alternative test is performed, namely the Mann-Whitney test
- 5. Analysis of clinical characteristics, side effects of OAE, and laboratory findings of complete blood count (hemoglobin, hematocrit, leukocytes, platelets, and type count), liver function (SGOT and SGPT), kidney function (urea and creatinine), and blood electrolytes (sodium, potassium, calcium, chloride) in pediatric epilepsy patients who are resistant to combination second OAE who re-use first line OAE as substitution therapy and who use standard therapy (secondary outcome). All existing data is processed and presented in a table consisting of mean and standard deviation or median and inter-quartile range, as well as frequency distribution.
- 6. Analyzing factors that affect the decrease in the frequency of late seizures (age, seizure onset, seizure type, family history of seizures, developmental delays, history of OAE, initial seizure frequency, initial EEG, brain structural abnormalities) in pediatric patients with resistant epilepsy combination of second line OAE who re-use first line OAE as substitution therapy (secondary outcome).

Data is categorical. Data is analyzed using Chi-square statistical test, if results do not meet the requirements then an alternative test will be performed, known as Fisher's multivariate test and further analyzed with multivariate test and logistic regression analysis. The significance level (α) is 5% and the research confidence level is 80%. Results will show statistically related if value of $p \le \alpha$ is obtained.

Ethics and dissemination

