The study will only be initiated after the protocol, consent form and the participants' information sheet are approved by The Ethics Committee of The Faculty of Medicine, Indonseia University-Cipto Mangunkusumo Hospital. We also apply for research permits at the 3 hospitals where the research will he held.

Informed Consent

Written informed consent will be obtained from the parents of participants. A potential participant whose more than 12 year-old at the time of clinic appointment will be given an informed assent. The writer will explain the details of the study and provide age-appropriate

participant information sheet to the participants and their parents. All questions about the study will be answered by the writer. Participants will be allowed sufficient time to decide whether to participate in the study or not. Before enrollment, the consent form will be signed by parents, or also by the participant who are 12 years old or above. If either the children or their parent decline to consent, they will not enter the study. The participant or their parent will keep a copy of the consent form, while the original copy will be kept by the chief writer in the recruitment file, a third copy will be kept in the patient's hospital record.

Discontinuation of study participation

Participants may choose to withdraw from the study, on their own or on the request of their parents/guardian, at any time during the course of the study. Subjects may withdraw for any reason without prejudice to his/her future medical care by the physician or at the institution. On withdrawal of consent, the date and reason for consent withdrawal will be documented. Participants' data collected up to the date of the withdrawal of consent may be included in the final analysis.

The investigator may also choose to withdraw a participant from the study if such a person does not comply with the procedure, did not participate in the study at least until the standard drug tapering-off phase, or died during the study. Withdrawn participants will not be replaced.

Study Records and Data Management

- Case report form

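### Children whose intervention is ended are classed as both non-responders and drop-outs, so the completer-only per-protocol analysis excludes treatment failures, and the 10% drop-out allowance does not fit that definition

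*Combined protocol and SAP*

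**What the plan says.** Study procedure sorts children by whether they finish. On finishers: "The children who complete all of the phases are categorized as responder". On children whose intervention is ended: "The subjects are categorized as non-responder, and will be dropped-out". Resignation, non-compliance and unrelated death are then listed as the other drop-out criteria, so being ended is itself one. The only explicit trigger for ending is a rise in seizures beyond 1.5 times the earlier frequency.

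Outcome evaluation (a) defines non-response more widely. It includes an unchanged frequency or a fall of less than 50%, and attaches no drop-out to it.

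Sample size requires 100 subjects and goes to 110: "An additional of 10% from the total number of subjects are needed as there is a possibility of those dropping out". It does not say which losses the 10% covers. Under Discontinuation of study participation: "Withdrawn participants will not be replaced".

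Statistical Analysis item 3 compares the incidence of increased seizure frequency between arms (CER - EER) by intention to treat, keeping everyone randomised, and per protocol: "Whereas per protocol analysis only includes subjects who complete the research to the end". Item 1, the chi-square test of responders, names no analysis set.

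**The concern.** A child whose intervention is ended has a known result: the treatment failed. Calling that child a drop-out lets an observed outcome be handled as a missing one. Two things follow.

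First, the per-protocol set is selected on the outcome it is meant to compare. An analysis that removes failures from both arms tends to show the arms as alike, and it can hide a real difference in either direction.

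Second, one drop-out figure has to cover both treatment failure and ordinary loss. The planning response rates already imply substantial failure, so the 10% cannot be judged until the plan says what it is for. Because item 1 names no analysis set, it is also unclear whether children labelled as dropped stay in the denominator of the primary test.

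**Working it through.** **Inputs.** Sample size: P1 = 0.95 (first-line), P2 = 0.70 (control), equal groups, 100 subjects plus 10%. Study procedure: completers are responders; ended children are non-responders and drop-outs. Item 3: the per-protocol set is completers only.

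**The plan's own figures.** 100 x 1.10 = 110, as stated. The printed formula with 1.96, 0.84 and the printed Q1 = 0.5 gives [(1.96 x sqrt(2 x 0.825 x 0.175) + 0.84 x sqrt(0.95 x 0.5 + 0.7 x 0.3)) / 0.25]^2 = 48.91, or 49 per arm. The plan prints 49.56, rounded to 50. Since 1 - 0.95 = 0.05, the same formula with Q1 = 0.05 gives 35.02, or 36 per arm.

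**Drop-out implied by non-response.** Non-response is 5% and 30%, mean (0.05 + 0.30)/2 = 0.175. With 55 per arm: 55 x 0.05 = 2.75 and 55 x 0.30 = 16.5, together 19.25, leaving 110 - 19.25 = 90.75. The text does not fix the share s of non-responders who are ended, so s is varied, and taken as equal in both arms (an assumption). Drop-out is 0.175 x s; completers are 110 x (1 - 0.175 x s).

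**Effect on per-protocol response.** If a share s of non-responders is removed, response among those left is p / (1 - s(1 - p)). For example, at s = 0.5 the control value is 0.70/0.85 = 82.4% and the first-line value is 0.95/0.975 = 97.4%.

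| Share s ended | Drop-out from non-response | Completers of 110 | Per-protocol response, first-line v control | Difference |
|---|---|---|---|---|
| 0 | 0% | 110 | 95% v 70% | 25 points |
| 0.50 | 8.75% | 100.4 | 97.4% v 82.4% | 15.1 |
| 0.57 | 10% | 99 | 97.8% v 84.5% | 13.3 |
| 0.75 | 13.1% | 95.6 | 98.7% v 90.3% | 8.4 |
| 1 (strict reading) | 17.5% | 90.75 | 100% v 100% | 0 |

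The 57% is 10/17.5. All rows are before any other loss.

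**Effect on CER - EER.** Failure in item 3 is an increase in seizure frequency. Children ended under the explicit trigger have had such an increase, so they are failures, and the completer rule takes them out of both CER and EER. This holds whether or not other non-responders are ended. On the strict reading no completer is a failure, and CER - EER = 0 - 0 = 0. The documents give no rate of increased seizures, so the size short of that extreme cannot be computed.

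**Effect on the intention-to-treat responder comparison.** The n in the formula counts responders and non-responders together, so an ended child is already in it. Power = Phi[(0.25 x sqrt(n) - 1.96 x sqrt(2PQ)) / sqrt(P1Q1 + P2Q2)], with P = 0.825, Q = 0.175 and Q1 = 0.05. This gives 94% at n = 55 per arm and 92% at n = 50.

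**The case against.** A reader might infer that every non-responder drops out, so that 17.5% is a minimum and 110 children leave 91 completers where 100 are needed. The documents do not support that.

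- The drop-out rule covers children whose intervention is ended, and its only explicit trigger is a marked rise in seizures. Outcome evaluation allows non-responders who do not worsen and does not drop them. Discontinuation of study participation lets the investigator withdraw a child who has not reached tapering-off, but that is discretionary. The flow-chart that may show where partial responders go is not reproduced.
- The 100 is a count of subjects with an outcome, and no section states a per-protocol size of 100. Intention to treat keeps everyone randomised.
- The 100 rests on the printed Q1 = 0.5. With 0.05 the formula needs 36 per arm, so 91 is not shown to be too few.
- The 95% is the control rate plus a difference chosen by the researcher. It is a design alternative and does not forecast 5% against 30% drop-out.

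All four points stand, and they limit the head-count argument. The strict reading still has support: titration runs until seizures have halved, the later steps follow from that, and no route to completion is described for a child who never gets there. None of the four points rescues the per-protocol definition, which removes known failures on either reading.

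**Conclusion.** The point holds as a conflict of definitions with a real consequence for the per-protocol analysis. If completing and responding are equated, per-protocol response is 100% in both arms and carries no information. If only half of the non-responders are ended, the planned 25-point difference shrinks to about 15 points. In item 3 the children ended for increased seizures are removed from the failure counts.

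The flat 10% is not reconciled with the drop-out definition. Non-response alone gives anything up to 17.5%, and 10% is enough only if at most 57% of non-responders are ended and no child leaves for another reason. These figures rest on the planned 95% and 70%, 55 children per arm and an equal ended share in both arms.

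No loss of sample size or power is shown for the intention-to-treat responder comparison, and neither 17.5% nor 91 should be quoted as a bound.

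**What to change.** Reconcile Study procedure, Outcome evaluation, Sample size and Statistical Analysis as follows. No extra children are needed.

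- Study procedure and Outcome evaluation: use one definition of non-responder, covering children who neither improve by half nor worsen enough to be ended. Remove the drop-out label from children whose intervention is ended, and record them as observed non-responders or failures.
- Statistical Analysis item 1: state that these children stay in the denominator of the responder test.
- Statistical Analysis item 3: keep them, as failures, in the denominators of both the intention-to-treat and the per-protocol analyses. A child whose intervention was ended under the protocol's own rule has followed the protocol.
- Sample size: state that the 10% covers only children whose outcome is unknown, through resignation, non-compliance, unrelated death or loss to follow-up.

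Do not write in expected per-protocol counts by arm (about 52 against 38). They would preserve the uninformative completer set and treat the design alternative as a forecast.

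The cost is wording, and a per-protocol response rate that will look less favourable because failures are counted.

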STUDY PROTOCOL

THE EFFICACY AND SAFETY OF FIRST LINE ANTI-EPILEPTIC DRUGS (AEDs) AS SUBSTITUTION THERAPY FOR CHILDREN WITH DRUG RESISTANT EPILEPSY

Protocol Number 22-09-1097

ABSTRACT

Background: Drug resistant epilepsy occurs around 30% of children with epilepsy. It is the failure to get seizure-free after combining two or more anti-epileptic drugs whether first- or second-line ones. Previous studies focus on the efficacy and safety between the two groups whether as add-on or substitution therapy mostly in newly diagnosed epilepsy children. However, the study that investigate first line Anti-epileptic Drugs (AEDs) as substitution therapy compared to second-line ones particularly among drug resistant epilepsy children is still lack. **Design**: It is an open-label, randomized controlled trial, which will be conducted in three referral hospitals in Jakarta, Cipto Mangunkusumo, Harapan Kita, and Fatmawati Hospital, from November 2022 until April 2023. The data will be collected from electronic medical record consisting of demographic, clinical characteristics, and brain CT scan or brain MRI, and diary cards that record daily drug consumption and adverse drug reaction. Self-administered QOLCE-55 questionnaire is used to assess the quality of life of the children. Furthermore, there will be EEG and laboratory examination prior and after intervention. The data will be recorded on Case Report Form that is filled by the researcher. Ethics committee approval is obtained from The Ethics Committee of The Faculty of Medicine, University of Indonesia-Cipto Mangunkusumo Hospital. Research permits would be issued by each institution where the study will take place.

Sample: There will be 100 participants, divided into 2 groups, the intervention and control. Fifty children in the intervention group will be treated with first line AEDs as the substitution therapy, while the other 50 participants in the control group will get second-line AEDs. The sample size is calculated based on the difference proportion of two independent groups.

Duration of the study: The study will take 14 weeks as a whole that consists of 6 phases including baseline, initial, titration, maintenance, tapering-of, stopping and another maintenance phase.

Introduction

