This protocol is intended for a multicenter open label experimental, randomized controlled trial on the efficacy and safety of using first line AEDs as substitution therapy in childhood drug-resistant epilepsy. It will prospectively follow 100 children up during 14 weeks that consist of baseline, intervention, and post-intervention phases. While the intervention consists of 6 steps, as described at the Figure 1 below.

[figure not shown]

Figure 1. Timeline of the intervention phases

The study will be conducted at pediatric outpatient clinic of 3 referral hospitals in Jakarta, Cipto Mangunkusumo Hospital, Harapan Kita Hospital and Fatmawati Hospital. Children who are diagnosed with drug-resistant epilepsy receiving levetiracetam or topiramate will be enrolled in the study. Enrollment begins as soon as the research ethics committee approval is obtained from The Ethics Committee of The Faculty of Medicine, University of Indonesia-Cipto Mangunkusumo Hospital. The study will be closed after the last recruited patient has been followed up for the required 14 weeks.

All recruited children will be examined for monitoring at the hospital where the intervention is initiated. To avoid selection bias, all patients who met the inclusion criteria are divided into two groups, the intervention and control groups. Prospective participants and their parents will be provided with information related to the study. Patients will then fill out an information sheet containing demographic data, comorbidities, developmental history, school history, history of drug consumption, as well as history of seizures and patient complaints. All the data will be extracted and recorded on the case report form. Patients and their parents should be informed that participation is voluntary and they are free to withdraw from the study at any time. They should also be informed that refusal to participate or withdraw from the study will not affect the quality of treatment received. In the event of their withdrawal, it will be explained that the data collected so far is irrevocable, and we will seek consent to use such data in the final analysis if necessary.

Study procedure

Study procedures are depicted in Figure 2. The patients who are eligible for the study and have given their consents, will be enrolled, divided into 2 groups, the intervention and control, then start the 3-day baseline phase. In this phase, data such as demographic, clinical characteristic

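### The protocol gives two enrolment totals, 100 and 110, and withdrawals are not replaced, so stopping at 100 drops the plan's own dropout allowance

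*Combined protocol and SAP*

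**What the plan says.** Four places in the combined protocol and SAP bear on the number to recruit.

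- **Abstract, Sample:** "There will be 100 participants, divided into 2 groups, the intervention and control". It puts 50 children in each arm and mentions no dropout allowance.
- **Study Design:** "It will prospectively follow 100 children up during 14 weeks".
- **Sample size:** "Based on the formula above, 100 research subjects are required". It continues: "An additional of 10% from the total number of subjects are needed as there is a possibility of those dropping out", and ends: "therefore a total of 110 subjects are needed in this study".
- **Discontinuation of study participation:** "Withdrawn participants will not be replaced".

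Statistical Analysis, item 3, defines two analyses. Intention to treat keeps every randomised child in the allocated arm and counts children lost to follow-up as failures. Per protocol includes only children who complete the study.

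**The concern.** All of these statements are current text, and none is marked as superseding another. A hospital working from the Abstract would stop at 100; one working from the Sample size section would stop at 110. The lower total omits the dropout allowance that the plan itself says is needed, and the rule against replacement means the loss cannot be made up later.

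The total also fixes when the trial ends, because Study Design closes the study once the last recruited child has been followed for 14 weeks. The trial is open-label, so an unsettled stopping count leaves room to choose between 100 and 110 with outcomes in view. Afterwards, either count could be reported as planned or as a deviation.

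**Working it through.** **Inputs.** From Sample size: P1 = 0.95, P2 = 0.70, P = 0.825, Q = 0.175, Zα = 1.96 (labelled one-way, but the two-sided 5% value), Zβ = 0.84 (80% power), Q2 = 0.3, Q1 printed as 0.5, dropout addition 10%. From the Abstract: 1:1 allocation, 50 per arm.

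**1. The plan's own figures.** The formula is n per arm = [(Zα√(2PQ) + Zβ√(P1Q1 + P2Q2)) / (P1 − P2)]².

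- First term: 1.96 × √0.28875 = 1.0532.
- Second term with Q1 = 0.5: 0.84 × √(0.475 + 0.21) = 0.6952.
- n = (1.7484 / 0.25)² = 48.91. The plan prints 49.56 and rounds to 50. The small gap does not matter here.
- Enrolment: 2 × 50 = 100, and 100 × 1.10 = 110. The 110 reproduces exactly.

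**2. Completers under each total, at 10% loss and no replacement.**

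| Enrolled | Per arm | Per-protocol completers | Per arm | In intention to treat |
|---|---|---|---|---|
| 100 | 50 | 100 × 0.9 = 90 | 45 | 100 |
| 110 | 55 | 110 × 0.9 = 99 | 49.5 | 110 |

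If the 10% means ten children rather than a rate among those enrolled, 110 − 10 = 100 remain, and ten is 9.1% of 110.

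**3. The requirement with the slip corrected.** 1 − 0.95 is 0.05, not 0.5.

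- Second term: 0.84 × √(0.0475 + 0.21) = 0.4263.
- n = (1.4795 / 0.25)² = 35.02, so 36 per arm and 72 in total.

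**4. Power among completers at 0.95 v 0.70** (two-sided 5%, pooled normal approximation). Power = Φ[(0.25√n − 1.96√0.28875) / √0.2575].

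- n = 45 per arm: Φ(1.23) = 89.1%.
- n = 49.5 per arm: Φ(1.39) = 91.8%.
- n = 50 per arm: Φ(1.41) = 92.0%.

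**5. Power under intention to treat.** Assume 10% loss in each arm, unrelated to response, with every loss counted as a failure. The rates become 0.95 × 0.9 = 0.855 and 0.70 × 0.9 = 0.63, a difference of 0.225, with pooled P = 0.7425. Then 2PQ = 0.3824 and P1Q1 + P2Q2 = 0.3571.

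- n = 50 per arm: Φ[(0.225√50 − 1.96√0.3824) / √0.3571] = Φ(0.63) = 73.7%.
- n = 55 per arm: Φ(0.76) = 77.8%.

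**The case against.** **Study Design may mean completers.** Following 100 children for 14 weeks is compatible with 110 enrolled and 100 finishing. This stands, so the contradiction rests mainly on the Abstract, which gives participants and arm sizes and cannot be read that way.

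**The 110 may be called the wrong inflation.** A reader might infer that the right figure is 100 / 0.9 = 111.1, or 112 in equal arms, and that neither stated total delivers 100 completers. The documents do not support giving this much weight. The Sample size section describes an addition of 10% to the required number, which is what 110 is. Only if 10% is a loss rate among those enrolled does 110 fall short, and then by about one child.

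**Losses do not leave the intention-to-treat analysis.** This is correct. The 90 and 99 describe the per-protocol set only. The number randomised still matters under intention to treat, because counting losses as failures narrows the difference between arms.

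**The trial may be called underpowered at 100.** A reader might infer this from 90 being ten below the stated requirement. That requirement is itself inflated by the Q1 slip. At the plan's rates, 45 completers per arm give 89.1%, above the planned 80%. The figures below 80% under intention to treat come from diluting the effect, occur at both 50 and 55 per arm, and depend on the assumed loss pattern.

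**Conclusion.** The point holds as an inconsistency. The Abstract's 100 and the Sample size section's 110 cannot both be the enrolment total, and with no replacement the lower one removes the plan's own allowance. The cost of stopping at 100 is about nine or ten completers: 90 remain, against 99 to 100 from 110. On power, the choice moves the completer analysis from 91.8% to 89.1%, both above 80%. Under intention to treat it moves power from 77.8% to 73.7%, both below 80%.

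These figures assume the plan's response rates of 0.95 and 0.70, a two-sided 5% test, and equal 10% loss unrelated to response. They also take the two analysis sets, defined under item 3 of Statistical Analysis, to apply to the responder comparison. The Study procedure section classes children whose intervention is ended as drop-outs too. If those children also leave the completer set, loss could exceed 10% by an amount the documents do not allow one to calculate.

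**What to change.** 1. Correct Q1 to 0.05 in the formula and restate the result (35.02, so 36 per arm, 72 in total). This is a requirement before any dropout allowance. It is not in itself a reason to recruit fewer, since power under intention to treat is already below 80% at 50 and 55 per arm.
2. Choose one enrolment total and use it in the Abstract, Study Design and Sample size sections.
3. State enrolled children and expected per-protocol completers separately. Examples are 110 enrolled (55 per arm) with about 99 to 100 completers, or 100 enrolled (50 per arm) with about 90 completers. Say whether the 10% is an addition to the requirement or a loss rate among those enrolled.
4. Restate power for the chosen total under both per protocol and intention to treat, with the loss assumption written out.

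The cost is wording and a short recalculation. No patients are needed beyond a total the protocol already states.
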